Research has shown that a successful implementation depends on interplay between the effectiveness of the implementation strategies chosen to support the implementation and characteristics of the implementation object, the implementers, the target population and the context of the implementation (Table 1).

Updated design of the implementation research

The project was planned to be conducted using a cross-over design in two counties in south of Sweden based on a feasibility/pilot study that was conducted during fall 2014 *co-created palliative care educational intervention through seminars for professionals in nursing homes*. Due to a more significant amount of drop-outs compared with expected (and for not receiving the total amount of applied foundation), the plan needed to be revised. The knowledge-based palliative care intervention was conducted as a non-randomized control trial, implemented over a six-month period in 30 nursing homes in two different counties in the south of Sweden (County A and County B). The data collection was made in two sequential periods in each county. First, the intervention was implemented in ten nursing homes in County A (Kronoberg County from April 2015), while ten nursing homes in County B served as a control group. Then, County B implemented the intervention (Skåne county from August 2016), and ten new nursing homes in County A, which had not received the intervention, were chosen as a control group. After the two sequential time periods were data from one intervention and one control group analysed. The selection through voluntary participation resulted in a mixture of both larger and smaller nursing homes within the two counties (cluster samples), as well as both from urban and rural areas.

Implementation object

According to the National Board of Health and Welfare, palliative care should be based on four cornerstones: symptoms relief, multi-professional cooperation, communication and relation as well as support to the next of kin (Socialstyrelsen 2012). The aim of palliative care is to reduce suffering and promote the quality of life for patients with progressive, incurable illnesses or injuries. The care should address physical, psychosocial and spiritual needs as well as provide support to the next of kin. The definition by the National Board of Health and Welfare closely

adheres to the definition of palliative care by the World Health Organization (WHO), (Socialstyrelsen 2013).

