Implementation intervention/strategies

The educational strategies will be based on *co-created palliative care educational intervention*, which consists of a series of seminars and coaching. The education has been planned together with staff, informal caregivers and patients. The educational material for use in the seminars has been developed as well as empirically tested in the feasibility study during the fall 2014. The strategies were tested in this feasibility study at four nursing homes in Kronoberg County during the autumn 2014, in order to understand how the implementation object can be translated into practice at nursing homes. Seven educational meetings were reduced to five as a result of the study.

Every seminar group meeting once a month includes different professions (unit manager, district nurse, assistant nurse, and other staff i.e. occupational therapist and physiotherapist). There will be 5 meetings with 8-10 participants in each group from each nursing home. The total intervention period is 6 months in each nursing home.

The educational strategies are based on the two national knowledge documents concerning palliative care in the end of life and the Swedish Register of Palliative Care (SRPC). The educational binder was developed based on the content in the two national knowledge documents and is used in this intervention. Each participant is provided a binder at the beginning of the intervention. The educational material consists of six themes; values in palliative care, symptom relief, dignity and a dignified death, collaborative co-creating care, support to next of kin and dialogue with older persons and next of kin about death and dying. The content of the different themes will have a common core for each nursing home but will be adjusted based on the expressed needs of each nursing home. In addition, there will be a list of references available for further self-studying by the participants.

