The seminar groups will be led by two experienced clinical nurses and researchers from the field of palliative care and geriatric care. The participants in the seminar groups will reflect together over the content of the developed binder of educational material and will relate it to their own work in order to identify areas suitable for changes and/or development. These areas will also be identified based on the Swedish Register of Palliative Care (SRPC). The knowledgebase for discussions in the seminar groups is seven selected quality indicators out of the total of 27 questions concerning essential aspects of palliative care. The seven quality indicators are: Prevalence of pressure ulcers, documented individual prescription when needed of opioid and anti-anxiety drugs, oral health assessment, talks about the substance and direction, pain analysis and regular estimation of pain intensity and regular use of instrument for symptom assessments.

The evaluation of the implementation

Data collection is made before and after the implementation, same time for intervention- and control groups. The implementation of the educational intervention will be evaluated by using qualitative and quantitative methods (see Table 2).

Table 2. Sub studies and data collection i Kronoberg County and Skåne County 2015 and 2016 for the implementation of knowledge based palliative care.

Subjects	Method	Selection in the implementation nursing homes	Selection in the control nursing homes*
Sub study 1: Older persons	Structured interview (based on WHOQOL-BREF (26 items), WHOQOL-OLD (24 items), P-CAT (13 items) and The Person-Centered Climate Questionnaire (17 items)	20 older persons were interviewed before and after three months after finished implementation	The same as for the implementation nursing homes
Sub study 2: Next of kin	Qualitative interviews participation and structured interview WHOQOL-BREF (26 items), WHOQOL-OLD (24 items)	20 next of kin before and three months after finished implementation	20 next of kin before and three months after finished implementation
Sub study 3: Next of kin	The participation of next of kin in palliative care at nursing homes (36 items) WHOQOL-BREF (26 items), WHOQOL-OLD (24 items)	100 next of kin before and after nine months	100 next of kin before and after nine months
Sub-study 4:	Psychometric study; test-retest, explorative factor analysis	See above	See above

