Sub study 5: Staff	Focus group interviews (preparedness for implementation)	20 staff divided into 3 groups before and after the implementation is finished	
Sub study 6: Staff	Questionnaires at two occasions: Experiences of palliative care (46 items), P-CAT (13 items) and the Person-Centered Climate Questionnaire (14 items)	100 staff before and after the implementation is finished	100 staff with 6 months in between
Sub study 7: Managers	Two individual interviews with managers (organic preparedness for implementation)	20 managers at different levels-, during the intervention and after six months	
Sub study 8: Implementation context	An ethnographic study: Observations and qualitative interviews	Observations on 28 occasions at 7 nursing homes with a strategic selection of qualitative interviews during the implementation	

THE OVERALL AND SPECIFIC AIMS

The overall aim of this research project is to evaluate the outcomes and effectiveness of the implementation method of a knowledge-based model for palliative care in nursing homes. The overall aim can be broken down into four specific research questions and nine different studies:

1. What is the outcome of the implementation intervention in terms of quality of life, participation and quality of care in older persons and next of kin at nursing homes before and after? (Study I, II-IV)
2. Investigates the staff's implementation process of palliative care and the role of the leadership and (Study V-IX).
3. Investigate which factors (barriers and facilitators) that affect the implementation process of this model (Study V, VII-IX).

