The Person-centered Care Assessment Tool (P-CAT) measures the extent to which an aged care setting is person-centered. The tool is primarily intended for use by staff but expanded with a version for the older person's self-reporting. The Swedish version of the P-CAT has been found to be valid, reliable, and applicable for further use (Edvardsson *et al.* 2010, Sjögren *et al.* 2012). Person-centered care is increasingly regarded as being synonymous with best quality care. In this project, both the staff version and the version for the older will be used.

The Person-Centered Climate Questionnaire: The Person-centered Climate Questionnaire exists both in a patient and a staff version. The instruments have been shown as being a valid and reliable contribution for assessing to what extent the climate of care environments is person-centered. The factors are safety, everydayness and hospitality. The instrument enables descriptions and comparisons of environments, exploration of correlates between person-centeredness and patient outcomes and/or measure results of various interventions (Bergland *et al.* 2015, Edvardsson *et al.* 2013).

The newly developed self-reported questionnaire was named Next of Kin Participation in Care (NoK-PiC): Before the start of this project, there was a complete lack of instruments designed to measure the participation of next of kin in palliative care in nursing homes. To deal with this, a questionnaire for next of kin's participation was developed before the beginning of the project. Literature reviews of previous research about the next of kin's participation was performed including all types of care in general as well as focus on palliative care and the care at nursing homes. The systematic literature review resulted in a questionnaire with 36 items about next of kin's participation in palliative care. The new questionnaire was psychometrical tested on 400 next of kin (Westergren et al. 2020).

Experiences of palliative care: The staff will also answer a questionnaire with 47 items, newly constructed to capture changes in health professionals' attitudes, knowledge and assessment of the quality of palliative care; before (one month's), and after finishing the implementation intervention. Validation of the questionnaire is ongoing (Östlund et al. 2014).

Focus group interviews and individual interviews

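### The follow-up tests treat staff and next of kin as independent although whole nursing homes got the intervention, so p<0.05 does not hold 5% error if change is correlated within homes

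*Protocol*

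**What the plan says.** **Allocation.** The Protocol (Updated design of the implementation research) describes a non-randomised controlled trial in 30 homes. In period 1, ten County A homes received the intervention and ten County B homes were controls. In period 2, County B received it and "ten new nursing homes in County A, which had not received the intervention, were chosen as a control group". The two periods were then pooled: "After the two sequential time periods were data from one intervention and one control group analysed". The same section calls the sample "a mixture of both larger and smaller nursing homes within the two counties (cluster samples". That is the only mention of clustering in either document.

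**Delivery.** Under Implementation intervention/strategies, seminars have "8-10 participants in each group from each nursing home", and their content "will be adjusted based on the expressed needs of each nursing home".

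**Sample.** Table 2 plans "100 staff before and after the implementation is finished" (Sub study 6) and "100 next of kin before and after nine months" (Sub study 3), with 100 in each control column. It does not say how many come from each home.

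**Analysis.** The SAP (Comparative studies) compares before with after inside each group by the Wilcoxon signed-rank test, at two-tailed p<0.05. For next of kin this is the only follow-up test of change that it spells out. For staff, the SAP (Logistic regression studies) adds a univariate logistic regression of group on improvement in P-CAT and PCQ-S, the only explicit between-group test of change. No home term, mixed model, GEE, robust variance, home-level analysis or ICC appears.

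**The concern.** Both tests take their variance from individuals assumed to be independent. Staff in one home share a manager, a workplace and, in the intervention group, a seminar series tailored to that home, so their changes may move together. Taking before/after differences removes stable differences between homes but not correlation in change.

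If that correlation is positive, the standard errors are too small. A shift confined to a few homes could then be reported as a significant change in the group. As p<0.05 is the only decision rule in these sections, nothing else in the plan guards against this.

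The point covers staff outcomes and the next-of-kin outcomes of Sub study 3. It leaves out the baseline age and gender comparisons, and the samples of 20 per group (older persons, and next of kin in Sub study 2). Those have only one or two people per home, and clustering matters little.

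**Working it through.** **Inputs from the documents.** Homes: 10 + 10 + 10 = 30. The total of 30 suggests that the same ten County B homes served as controls in period 1 and as intervention homes in period 2. That is an inference. It gives 40 home-periods, 20 per pooled group. The Ethical considerations section speaks of two control-only homes, whereas the design section implies ten; the two need reconciling.

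**Number per home (m).** 100/20 = 5. Other anchors:
- 254 next of kin in the WHOQOL-BREF psychometric work (240 + 14 excluded): 254/40 = 6.35.
- "The new questionnaire was psychometrical tested on 400 next of kin": 400/40 = 10.
- If the 100 came from only ten homes: 100/10 = 10.
- After drop-out, m = 3 is plausible.

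**Assumed.** ICC of change of 0.02, 0.05 and 0.10; the documents give none.

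**Formula for a within-group test.** DE = 1 + (m − 1) × ICC; actual error = 2 × [1 − Φ(1.96/√DE)]. The plan has no sample-size figure to reproduce. At ICC 0 the formula returns its nominal 5.0%. Example, m = 5 and ICC 0.05: DE = 1 + 4 × 0.05 = 1.20; 1.96/√1.20 = 1.789; error 7.4%.

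| m | DE at ICC 0.02 / 0.05 / 0.10 | Error by formula | Wilcoxon, simulated |
|---|---|---|---|
| 3 | 1.04 / 1.10 / 1.20 | 5.5 / 6.2 / 7.4% | 5.3 / 5.9 / 6.9% |
| 5 | 1.08 / 1.20 / 1.40 | 5.9 / 7.4 / 9.8% | 5.8 / 7.3 / 9.4% |
| 6.35 | 1.11 / 1.27 / 1.54 | 6.3 / 8.2 / 11.4% | not run |
| 10 | 1.18 / 1.45 / 1.90 | 7.1 / 10.4 / 15.5% | 7.4 / 9.8 / 14.7% |

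The simulation used normal change scores, zero mean change, equal home sizes and 20,000 runs per setting. At m = 5 and ICC 0 the Wilcoxon test gave 4.8%. Ten homes of 10 gave 6.6 / 10.0 / 15.2%. Reuse of County B homes does not alter these figures, because each pooled group contains 20 different homes.

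**Staff logistic test.** Here reuse matters. A home effect that persists across periods enters both groups and partly cancels. With full sharing, the 10 common homes reduce the design effect to 1 + (m/2 − 1) × ICC. The ICC of the binary improvement is (2/π) × arcsin(ICC) = 0.013, 0.032, 0.064. At m = 5 the formula gives 5.2 / 5.6 / 6.1% shared and 5.6 / 6.5 / 8.0% independent. Simulated, with 50% improving unless stated:

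| m | County B home effects across periods | Error at ICC 0.02 / 0.05 / 0.10 |
|---|---|---|
| 3 | independent | 5.5 / 5.9 / 6.7% |
| 5 | independent | 5.9 / 7.0 / 8.8% |
| 5 | half shared | 5.8 / 6.8 / 8.0% |
| 5 | fully shared | 5.7 / 6.0 / 6.8% |
| 5 | fully shared, 40% improving | 5.2 / 5.4 / 6.3% |
| 10 | independent | 6.4 / 8.6 / 12.0% |
| 10 | fully shared | 5.6 / 6.4 / 8.2% |

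At m = 5, ICC 0 and 50% improving, this test gave 5.3%. That small excess comes from the Wald test on discrete counts, so clustering should be measured from 5.3%, not 5%. At m = 5 it adds 0.6, 1.7 or 3.5 points with independent effects and 0.4, 0.7 or 1.5 with fully shared effects.

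**The case against.** The strongest reply is that the size is unknown and may be small. Several parts of it stand.

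- **Logistic baseline.** Measured from 5.3%, clustering adds little to the only between-group test if County B effects are shared and the ICC is low.
- **Ten per home is a weak anchor.** Seminar attendance is not the questionnaire sample, and the 400 next of kin are a psychometric sample. The Protocol reports more drop-out than expected. Three to five per home is better supported, so the larger figures are an upper range.
- **Mechanism.** Tailored seminars exist only in intervention homes. With clustering in that group alone, m = 5 and 50% improving, the logistic error is 5.8 / 6.4 / 7.3%. Control homes can still share change through staffing or management, but the documents do not show that they do.
- **Which null.** Correlation created by tailoring is itself variation in the intervention's effect. The inflation then applies to the null of zero average change across homes, not to no change in any home. The average is what a group-level result is read as.
- **Next of kin** do not attend the seminars, and their ICC may be near zero.

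None of this supplies the missing adjustment. It bears on how large the error is. A 5% claim that is valid only at zero correlation needs that assumption stated and checked, and the plan does neither.

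**Conclusion.** The concern holds, conditionally. The omission is certain: the documents describe cluster sampling and home-level delivery, and neither follow-up test accounts for home. The consequence depends on positive within-home correlation of change. At ICC 0 there is no inflation from clustering.

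At 3 to 5 people per home and ICC 0.02 to 0.10, the Wilcoxon tests run at about 5.3% to 9.4%. The logistic test at 5 per home runs at about 5.7% to 8.8% when half improve. At 10 per home the upper ends are 14.7% and 12.0%. The ICC, the number per home and the linkage of County B homes are assumed or inferred.

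This should be fixed. It does not by itself overturn the trial's findings, but p-values just under 0.05 for staff or next of kin cannot be taken at face value.

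**What to change.** 1. **Main analysis.** For staff and next-of-kin outcomes, replace reliance on within-group tests with a between-group model (follow-up adjusted for baseline, change, or improvement, on group) including county and period. Account for home by a mixed model, or by GEE or cluster-robust errors with a small-sample correction. Without the correction, simulated error was 5.0% to 6.3%; with it, the model on change gave 3.7% to 4.9%.
2. **Linkage.** Give each County B home one identifier across both periods, and report the ICC for each outcome.
3. **Smallest change.** Cluster-robust errors by home can be applied to the staff regression as written (simulated error 4.5% to 5.6%). Making group the predictor helps interpretation but is not needed for valid error.
4. **Home-level check.** Using home means, take half of [(County A period 1 mean − County A period 2 mean) + the mean within-home difference, period 2 − period 1, in County B]. Simulated error was 4.6% to 5.1%.
5. **Within-group p-values, if kept.** Base them on home mean changes (4.8% to 5.3%).
6. **State the limit.** Group coincides with the county-by-period interaction, so county-specific time trends remain confounded with the effect. If 1% of variance lay there (an assumption), the home-level check would still reject 9% to 10% of the time at 5 per home.

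**Cost.** The SAP was updated in October 2020 and is written in the past tense, so this is a re-analysis and should be labelled post hoc. No new data are needed if home and period were recorded for each participant, which the documents do not state. Within a group at ICC 0.02 / 0.05 / 0.10, standard errors grow by √DE: 4 / 10 / 18% at 5 per home and 9 / 20 / 38% at 10. The effective size is 100/DE, so 100 people carry the information of about 93 / 83 / 71 or 85 / 69 / 53.

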The evaluation consist of 8 studies and involves four implementation outcomes in accordance with the framework proposed by Proctor *et al.* (2011): **Acceptability** - The perception among implementers (nursing home staff and managers) that a given knowledge-based practice (palliative care in nursing homes) is agreeable, towards benefit or satisfactory; **Appropriateness** - The perceived fit, relevance or compatibility of an knowledge-based practice (palliative care), for a given practice setting, provider, or consumer (older persons and their next of kin); **Feasibility** - The extent to which an knowledge-based practice (palliative care) can be successfully used or carried out within a given agency or setting (nursing homes); and **Fidelity** - The degree to which an knowledge-based practice (palliative care in nursing homes) was implemented as it was prescribed in the original protocol (the knowledge documents concerning palliative care).

Participants in studies

The persons asked for participation in this study, i.e. older persons, next of kin, staff and leaders are recruited from the included nursing homes in both Skåne and Kronoberg counties. The persons are selected consecutively until the stipulated figures are reached (Table 2).

Methods and instruments

The following methods and instruments will be used in this project:

Questionnaires

Quality of life: The WHOQOL-BREF questionnaire (WHO, Manual 1996) and the WHOQOL-OLD questionnaire (WHO, Manual 2006) assessed quality of life. The older persons and next of kin will answer to the questions in a structured interview. The WHOQOL-BREF is often used together with the WHOQOL-OLD module and both are psychometric tested by the WHOQOL Group (Power *et al.*, 1999). The WHOQOL-OLD module have been validated for old people in several countries, for example Sweden (Power *et al.* 2005) and can be used in a wide variety of studies including cross cultural investigations, population epidemiology, health monitoring, service development, and clinical intervention trials in which issues about quality of life are crucial (WHO, Manual 2006). The project has acquired permissions from WHO to use these questionnaires and in order to make it easier to answer the questionnaires, the answer alternatives will be enlarged on a separate paper and used during the interview.

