Official title of the study:
Implementation of Knowledge-Based Palliative
Care for Frail Older Persons in Nursing Homes

NCT number: NCT02708498

Date of the document: April 8, 2015, updated October 6, 2020

Statistical Analysis Plan

Simple descriptive statistics:

Median-Mean, Quartiles, Percentage

These are applied to all quantitative studies.

Baseline study:

Target population: Older people

Instruments: Characteristics of older participants, WHOQOL-BREF & WHOQOL-OLD

The data were analysed in one descriptive and one analytical section. In the descriptive section, numbers and percentages were calculated on a group level. A mean score was calculated for each domain using both the raw domain score, a standardized domain score (SDS) with the raw domain score divided by the number of items in the domain (1-5) and a transformed domain mean score (TDS 0-100) according to the instrument manuals. The different calculations were performed to enable comparison of our results with those from other studies.

In the analytical section, the participants were divided into two age groups (66-88 years and 89-102 years) by the population median age and gender (female and male). To examine differences in quality of life, a comparison of medians was conducted using the Mann-Whitney U test.

Comparative studies (Baseline and Follow-up):

Target population: Older people, next-of-kin, staff

Instruments: PCAT, PCQ-S, PCQ-P, WHOQOL-BREF, WHOQOL-OLD, Your experience of palliative care, Next-of-Kin Participation in Care (NoK-PIC)

The selection of the statistical tests to analyze data other than the descriptive statistics was based on whether the data were distributed normally and the scale level of the instruments. The Mann-Whitney U-test and the Kruskal-Wallis test was applied to compare the baseline characteristics of the two groups. The quantitative data collected from questionnaires were analyzed using within-group comparisons (the data from after the intervention period were compared with the data from before the intervention period in the intervention group and the control group) by Wilcoxon signed rank test.

Either Pearson's chi-square test or Fisher's exact test was used when the expected value was less than 5.

A two-tailed p-value of <0.05 was regarded as statistically significant.

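### No rule covers next of kin whose resident dies or leaves the home before the nine-month follow-up, and the planned within-group tests cannot separate the consequences from the intervention

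*Protocol*

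**What the plan says.** **Timing.** Sub study 3 in Table 2 of the protocol plans "100 next of kin before and after nine months", with the same wording for intervention and control homes. Sub study 2 plans "20 next of kin before and three months after finished implementation", again in both columns. The protocol also says: "The total intervention period is 6 months in each nursing home". Three months after the end is therefore 6 + 3 = 9 months after the start, and the two sub-studies agree if Sub study 3 counts from baseline. The two groups are measured in parallel: "Data collection is made before and after the implementation, same time for intervention- and control groups".

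**Who is followed.** Under Participants in studies, the participants "are recruited from the included nursing homes in both Skåne and Kronoberg counties", consecutively until the quotas are filled. No condition refers to the resident's status at follow-up.

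**Outcomes.** Sub study 3 uses NoK-PiC, WHOQOL-BREF and WHOQOL-OLD. NoK-PiC was developed because no instrument existed that was "designed to measure the participation of next of kin in palliative care in nursing homes".

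**Analysis.** Under Comparative studies (Baseline and Follow-up), the SAP says that "the data from after the intervention period were compared with the data from before the intervention period", separately in each group, by Wilcoxon signed rank test at two-sided 0.05. The Mann-Whitney and Kruskal-Wallis tests there are for baseline characteristics. The only model that relates change to group is the logistic regression, which covers staff instruments only.

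**Drop-out.** The protocol reports more drop-outs than expected, without reasons. The SAP compares drop-outs with participants inside each group, as a check on external validity.

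**The concern.** The next of kin are in the study because of a frail nursing-home resident. The SAP's baseline study gives the older participants' ages as 66 to 102, split at the median into 66-88 and 89-102. Some deaths and moves within nine months are foreseeable, and both bear on what is measured. Once the resident has died or left, NoK-PiC has no current care in the home to refer to, and a quality-of-life answer may reflect bereavement. The protocol's Palliative care section itself links rapid decline in the older person to more stress on next of kin.

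The next-of-kin part of the first research question is at stake. A fall in quality of life or participation could reflect deaths alone, a real gain could be masked, or the result could describe only families whose resident survived. From the documents, a reader cannot tell which of these the nine-month change represents.

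**Working it through.** **No planned figure to reproduce.** The documents give no power, effect size, SD or death rate for next of kin, and the 100 per group is a quota without a derivation. What follows is an illustration.

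**Two ways a resident's death can enter the result.**
- *Bereaved next of kin respond.* With bereaved share m and bereavement effect b (in SD of the score), one arm's mean change shifts by m × b when the intervention does nothing.
- *Bereaved next of kin leave.* The pairs come only from next of kin of surviving residents. The direction and size of this selection cannot be computed from the documents.

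**Size in the first case, one arm, Sub study 3.** From the protocol: n = 100 pairs. From the SAP: two-sided alpha 0.05. Assumed: m = 15-35%, b = 0.3-0.5 SD downward, before/after correlation 0.7.
- Shift: 0.15 × 0.3 = 0.045 SD, up to 0.35 × 0.5 = 0.175 SD.
- SD of change: √(2 × (1 − 0.7)) = 0.775 SD.
- Low end: z = √100 × 0.045 / 0.775 = 0.58, so two-sided rejection is about 9%.
- High end: z = √100 × 0.175 / 0.775 = 2.26, so two-sided rejection is about 62%.

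This is a normal approximation to the paired test. The 9% counts rejections in either direction. Declines alone are about 8.4%, to be set against a nominal 2.5%.

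**Check with the planned test.** The Wilcoxon signed rank test was simulated with 100 pairs, no intervention effect and 4,000 runs per setting. Here b is in SD of the *change* score, so the range is a different and wider set of assumptions.

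| Bereaved share | b | Rejection rate |
|---|---|---|
| 10% | 0.5 | 8% |
| 20% | 0.5 | 16% |
| 30% | 0.5 | 28% |
| 20% | 1.0 | 40% |
| 40% | 1.0 | 93% |

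**Between-group comparison.** With the same b in both arms, the bias in the difference in change is (m_intervention − m_control) × b. It is zero if the bereaved shares are equal. If they sat at opposite ends of the assumed range, it would be (0.35 − 0.15) × 0.3 = 0.06 SD to (0.35 − 0.15) × 0.5 = 0.10 SD.

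**Sub study 2.** With 20 per group and partly qualitative interviews, the calculation for 100 pairs does not apply. The same assumed shares would mean 0.15 × 20 = 3 to 0.35 × 20 = 7 bereaved next of kin per group.

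**The case against.** The strongest reply is that the documents never say bereaved next of kin are re-measured. A reader might infer from the fixed interval that everyone is measured again whether or not the resident is alive. That is an inference from silence. A bereaved relative has no current care to rate on NoK-PiC, and the unexpected drop-out could include such people. This part of the reply stands. It changes the form of the problem, from a mix with bereavement to selection of survivors' families, but does not remove it. The SAP's drop-out comparison does not settle the matter, because it is not tied to resident status.

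The second reply is that a concurrent control group is measured at the same times, so bereavement common to both arms would show in both. This is correct for a between-group comparison of change with equal bereaved shares and effects. However, the SAP specifies no such comparison for next of kin. The arms are also non-randomised: the homes volunteered, and in each period the two groups lie in different counties, so equality cannot be presumed.

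Third, every input to the illustration except n and alpha is assumed, including the direction of the effect. Given the stress that the protocol reports during rapid decline, quality of life need not be lower after a death than at baseline. This stands, so the percentages are not estimates for this trial. Nor can the figure of up to 40% in the protocol serve as a death rate, since it is the share of all deaths that occur in nursing homes.

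**Conclusion.** The gap holds in this form: handling of next of kin whose resident dies or leaves before follow-up is undefined, the change is tested in one pooled paired test per group, and no between-group comparison of change is written that would use the control group. The nine-month result therefore either mixes in bereavement or is limited to next of kin of surviving residents, and the planned tests can separate neither from the intervention.

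The 9% to 62% applies to one arm of Sub study 3 read alone, only if bereaved next of kin stay in the analysis, and only under the stated assumptions. It should not be read as the trial's false-positive rate. In a between-group comparison the bias shrinks to the difference in bereaved share times the effect, which need not be zero here. The point should be addressed before conclusions are drawn about next of kin. Confidence is medium, because what happened to bereaved next of kin is not documented.

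**What to change.** 1. State how next of kin were handled when the resident had died or moved before follow-up.
2. Obtain resident status at follow-up (alive in the home, moved, dead) from the homes' records, and report it by arm for both respondents and drop-outs.
3. Keep the results for all respondents.
4. As a sensitivity analysis, labelled as such before it is run, show NoK-PiC and WHOQOL change separately for next of kin of residents still living in the home, where NoK-PiC has a current referent, and for bereaved next of kin. In Sub study 2, describe these groups without testing.
5. Add a comparison of change between the intervention and control groups for next of kin.

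**Cost.** The documents describe data collection in the past tense, so status must be retrieved retrospectively. The strata are smaller: with 10, 20, 30 or 40% bereaved (assumed), 100 pairs per group become 90, 80, 70 or 60. For an assumed between-group difference of 0.4 SD of change, power falls from 81% to 77, 72, 66 or 59%. The living-resident subset conditions on an event after baseline that may differ between arms, and must be labelled so; this is why it should not replace the all-respondent result. If status cannot be recovered, state that as a limit on the next-of-kin conclusions.
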